4.0 Study Intervention(s)/Interaction(s)

4.1 Description: Researchers will interact with study participants during Phase I and Phase II (Table 1). In Phase I, researchers will enroll 20 PWMC and their care partners to participate in a dyadic interview session. The dyadic interviews will occur via the HIPAA-compliant video conferencing platform, Zoom. The interviews will begin with questions

SOCIAL PROTOCOL (HRP-580)**PROTOCOL TITLE: A Mobile Informatics Solution to Aid in Memory****VERSION DATE: 7/1/2022**

about the participants' technology use prior to and during the COVID-19 pandemic then participants will watch a brief instructional video followed by a question and answer session on the smartwatch technology, a verbally administered survey, and end with a semi-structured discussion about the SR. In Phase II, researchers will enroll 100 PWMC and their care partners to participate in initial, 3-month, and 6-month surveys. Half of the dyads will be randomly assigned to receive the smartwatch technology for a 6-month period and the other half will be randomly assigned to the usual care control group. 20 PWMC and their care partners who receive the smartwatch technology will be asked to participate in a semi-structured interview in the month following their 3 or 6-month survey.

Table 1. Phase I and II Schedule for AME Developers and UMN-Affiliate Researchers

	Months 1-6	Months 7-12	Months 13-24	Months 25-36
Project Management: Weekly Web Conference and Annual In-Person Meetings	•	•	•	•
● Recruit and train RA ● Build Smartwatch Reminder ● Data management and entry protocols	•	○	○	○
Phase I (Months 1-12)				
● Enroll 20 PWMC and their care partners	•	○		
● Complete dyadic interviews	•	○		
● Analyze Phase I qual/quan data ● Refine Smartwatch Reminder content and protocol for Phase II	○	•		
Phase II (Months 12-36)				
● Enroll 100 PWMC and their care partners			•	○
● Complete initial, 3-month, 6-month, and embedded qual data collection			•	•
● Analyze qual/quan data			○	•
● Disseminate Phase II findings			○	•

NOTE: RA = research assistant; PWMC = persons with memory concerns; qual = qualitative; quan = quantitative; • = primary focus; ○ = secondary focus

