to the SR along with the training procedures or an attention control group. Randomization (participant is assigned to either the treatment or control condition) will be completed via an a priori list generated from <http://randomizer.org> by [name]. For those in the SR treatment group, the research coordinator will schedule a time to introduce the SR to the PWMC and the care partner via Zoom or telephone.

To ensure blinding is maintained, the RA will not have access to the password-protected database containing participants' group assignment, and will not review survey data completion (which would un-blind the RA since all of the treatment participant follow-up surveys will contain the system review and all control participant follow-up surveys will not). Additionally, opaque, sealed envelopes will be created for the research coordinator to reveal which group each participant was randomized into. The outside of each envelope will be labeled with a dyad's ID and the inside will contain their group assignment, which will ensure integrity of the randomization order since no one will be able to change the order once the envelopes are created.

5. **3-month survey or contact call:** A survey will be administered (either online in Qualtrics or via mail, if preferred) by the RA to all participating care partners and PWMC 3 months following enrollment. A brief disposition survey will be administered before the 3- and 6-month follow-up surveys to determine if the PWMC has moved or passed away. A system review of the SR will be assessed via a checklist and open-ended questions (see Appendix) and will be sent only to dyads in the intervention group in their follow-up survey (the RA will remain blinded because they will email participants personalized links to the survey which do not indicate whether the participant is receiving the SR system review or not in their follow-up survey). The attention control group will receive a 3-month contact call from the research coordinator. Based on our prior experience, PWMC and care partners in an attention control group will often seek information and psychosocial support during these calls. We will provide free information resources (e.g., brochures or websites of the Alzheimer's Association). See section 10.2 about re-assessing each PWMC's capacity to consent at each time point.

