6. **6-month survey or contact call:** A survey will be administered (either online in Qualtrics or via mail, if preferred) by the RA to all participating care partners and PWMC 6 months following enrollment. A brief disposition survey will be administered before the 3- and 6-month follow-up surveys to determine if the PWMC has moved or passed away. Additionally, a system review of the SR will be administered by the RA to participating care partners and PWMC in the intervention group 6 months following enrollment (while remaining blinded). The attention control group will receive a 6-month contact call from the research coordinator.
7. **Data tracking for 6 months:** Detailed data on frequency and duration of use by PWMC and their care partners will be tracked directly by the SR, allowing for an analysis of exact utilization and practicality (i.e., how long and often PWMC and their care partners actually use the technology). This data will be shared with us securely via Box by AME.
8. **Semi-structured interview:** 20 semi-structured interviews will take place up to one month after completion of the final 6-month follow-up survey with intervention group participants only. Due to a change in study funding and timeline, as of 9/1/23, to meet the

SOCIAL PROTOCOL (HRP-580)

PROTOCOL TITLE: A Mobile Informatics Solution to Aid in Memory

VERSION DATE: 7/1/2022

20 semi-structured interviews, some semi-structured interviews will now take place following the 3-month follow up survey with intervention participants. Dyads will complete only one interview at 3 or 6 months, not at each time point.

Note: Baseline and follow-up surveys and interviews will be in a format that is convenient to care partners and PWMCs: through online or mail formats, whichever is desired by the individual. Each baseline survey is anticipated to take no more than 45 minutes to complete with follow-up surveys expected to take approximately 20-30 minutes to complete. If the PWMC has passed away or moved into a long-term care facility as determined by the brief disposition survey at 3- or 6-months, the PWMC would not be administered any additional surveys and the care partner would receive shortened follow-up surveys if they agree to continue, depending on the person with memory concern's scenario (bereavement or transition to a long term care/assisted living facility).

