The RA will complete disposition calls or emails ± 7 days prior to a scheduled follow-up survey. The RA will contact care partners within 1 week of a missed survey to resend, and update participants' contact information as needed throughout the project. RA will follow up with CG and PWMC via email reminders at 1, 2 and 3 weeks past the date a survey was sent if it is still incomplete. Additionally, at 3 weeks RA/RC will try to contact dyad via phone. If no response, participants will be considered lost to follow up (LTFU) for that time point.

Note: If LTFU occurs at baseline, the dyad will be withdrawn from study as they were not randomized.

An annual project newsletter will be sent to all participants to provide updates on study progress as well as provide seasonal caregiving tips. Finally, in order to provide additional rapport and incentive to participate in the attention control group, all PWMC and care partner dyads in the proposed project will be provided with up to a \$100 participation incentive following completion of their 6-month survey (see more information in Payment section 12.5). Those in the treatment group who are selected for and complete a semi-structured interview will receive an additional \$50 participation incentive.

Phase II Data Collection.

The RA will administer the baseline and follow-up surveys at 3- and 6-months, and will be blinded to randomization. Completion of these follow-ups may occur outside of the timeframe for initial contact based on participant scheduling needs.

Baseline, 3-Month and 6-Month Survey. The RA will administer all surveys (see Appendix). The surveys are designed to collect information from both PWMC and care partners. The selected measures have strong psychometric properties, sensitivity to change, and clinical relevance in the evaluation of health technology such as SR. Our past experience in distributing surveys of similar length indicate that they take PWMC and their care partners approximately 20-45 minutes to complete. Mean and sum scores will be calculated for all scales.

SOCIAL PROTOCOL (HRP-580)

PROTOCOL TITLE: A Mobile Informatics Solution to Aid in Memory

VERSION DATE: 7/1/2022

- Context of care (baseline only). Care partners will complete context of care variables include geographic location, time since diagnosis, type of dementia diagnosis, Medicaid status, living arrangement of the PWMC, and demographics of the PWMC and the care partner.

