- Community engagement. A 15-item survey developed specifically for the project will evaluate the PWMC's typical social interactions and destinations accessed outside of the home. The survey evaluates average frequency of leaving the home; socializing in-person with family and friends; and destinations accessed including senior centers, gyms and recreational facilities, educational classes, libraries, faith services, club meetings, coffee shops/cafes, and parks. Following the 15-item survey, an open-ended question to be applied post-baseline asks in which situations the SR system was and was not useful, and why.
- Caregiving Burden. A short version of the Burden Scale for Family Caregivers (BSFC-s) is a valid measure of subjective burden among family caregivers and is measured using 10-items on a 4-point scale (54).

Phase II will also feature 20 semi-structured interviews with purposively sampled dyads who are randomly assigned to receive SR. These interviews will take place up to one month after completion of the final 6-month follow-up survey. As of 8/31/2023 due to funding and timeline changes, interviews may also take place up to one month after completion of the 3-month follow-up survey. Dyads will only complete an interview at one time point (not both). It was determined that interviews at 3 months will be as rich in data as the 6 month surveys. A sequential mixed methods sampling approach will be utilized(36) where the results of the first methodological strand will inform the selection of participants in this second methodological strand. Specifically, the academic collaborators (led by [name]) will purposively select 10 dyads who report average system review checklist scores between 4 and 5 (i.e., SR met their needs) and 10 dyads who indicate average system review checklist scores of 3 and below (i.e., neutral and below regarding SR meeting their needs). A stratified purposive sampling approach will be applied: the academic collaborators will identify family care partners of different kin

SOCIAL PROTOCOL (HRP-580)

PROTOCOL TITLE: A Mobile Informatics Solution to Aid in Memory

VERSION DATE: 7/1/2022

relationship (care partner is spouse vs. adult child), PWMC with varying dementia severity (middle versus late stage dementia symptomatology), caregiver gender, and racial or ethnic background of caregivers to participate.

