The open-ended responses of the semi-structured interviews will provide in-depth information on the reasons why dyads felt SR did or did not enhance their interactions with each other and their friends and family. The research assistant will schedule and conduct the semi-structured interviews and will digitally record each one with permission. If permission to record the interview is not granted, relevant field notes will be taken during and immediately following the interview. Audio recordings will be transcribed by a professional transcriptionist into a Microsoft Word file which will then be uploaded to NVivo (37) for subsequent analysis. This mixed methods design will allow the research team to link the efficacy results of the study to the thematic categories developed from the semi-structured interviews.

5.3 Follow-Up: N/A: The study team will not conduct long-term follow up with study participants.

5.4 Individually Identifiable Health Information: N/A: The research team will not access any medical records or other sources of private information about participants, apart from the information provided directly by participants in surveys, interviews, or direct communication with research team members.

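### The research assistant described as blinded at the 6-month follow-up is also assigned to interview smartwatch-arm dyads, some of them before that follow-up

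*Combined protocol and SAP*

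**What the plan says.** **Blinding.** Under Phase II Data Collection, Section 5.2 states: "The RA will administer the baseline and follow-up surveys at 3- and 6-months, and will be blinded to randomization". Item 6 of the Study Procedures repeats the claim for the 6-month contact. There the RA also sends the SR system review to dyads "in the intervention group 6 months following enrollment (while remaining blinded").

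**Safeguards.** Under item 4, "the RA will not have access to the password-protected database" that holds the assignments, and the RA does not look at survey completion. The research coordinator learns the assignment from opaque sealed envelopes. Item 5 adds that the emailed survey links do not reveal the arm.

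**Follow-up contacts.** The notes after item 8 give the RA the disposition call or email, the resending of missed surveys and the reminders at 1, 2 and 3 weeks. The telephone attempt at 3 weeks falls to the RA or the coordinator.

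**Interviews.** The final part of Section 5.2 says: "The research assistant will schedule and conduct the semi-structured interviews and will digitally record each one with permission". The 20 interviews are with "purposively sampled dyads who are randomly assigned to receive SR".

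**Timing.** Item 8 says that "some semi-structured interviews will now take place following the 3-month follow up survey with intervention participants". The Phase II Data Collection text says that "interviews may also take place up to one month after completion of the 3-month follow-up survey", and Section 4.1 has the 20 dyads "asked to participate in a semi-structured interview in the month following their 3 or 6-month survey". The revision history entry for version 19 says that other procedures are unchanged.

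**The concern.** An interview about the SR, held only with dyads that received it, discloses the arm. Being handed the list of dyads to schedule is enough. While all interviews came after the 6-month survey, this did not matter: the dyad's last survey was already in. Once some interviews moved to the month after the 3-month survey, the role that conducts them goes on to handle the same dyads' 6-month disposition contact, survey and reminders. The statement that this role remains blinded was not changed.

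Six months is the time point that counts, because Sections 3.1 and 17.1 base the efficacy analysis on baseline and 6-month data. If one person does both tasks, a report that a blinded RA ran the 6-month follow-up would be untrue for these dyads. The exposure is also one-sided, since no control dyad is interviewed. Any effect would run through contact and chasing: how a disposition call is conducted, or how hard a non-responder is pursued before being counted as lost. Section 17.2 leaves little room for uneven retention, with 97 dyads required, 100 enrolled and attrition assumed below 3%.

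**Working it through.** There is no plan figure to reproduce here. The check is a comparison of texts followed by simple exposure arithmetic.

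**Step 1: who does what, and when**

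| Task | Role named | Arms | Place in Section 5.2 |
|---|---|---|---|
| Open allocation envelopes | Coordinator | Both | Item 4 |
| Introduce the SR | Coordinator | SR | Item 4 |
| 3-month and 6-month control contact calls | Coordinator | Control | Items 5 and 6 |
| Month-3 interview | Research assistant | SR only | Item 8; Phase II Data Collection |
| 6-month disposition contact | RA | Both | Notes after item 8 |
| 6-month survey | RA, stated to be blinded | Both | Item 6; Phase II Data Collection |
| Reminders at 1, 2 and 3 weeks | RA | Both | Notes after item 8 |
| Telephone attempt at 3 weeks | RA or coordinator | Both | Notes after item 8 |

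The month-3 interview and the 6-month contacts fall to the same role, and the interview comes first.

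**Step 2: do the safeguards cover it?** Barring the RA from the assignment database, barring review of survey completion, sealing the envelopes and using neutral links each close a documentary route to the assignment. None closes the route through a conversation about the device.

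**Step 3: is the work divided elsewhere?** Revision 11 in the revision history adds two research assistants. No section says that one interviews and the other follows up, and none limits the blinding statement.

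**Step 4: how many dyads**

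- Inputs: 100 dyads, half assigned to SR (Section 5.2, Phase II Sample Size), so about 100 × 1/2 = 50 SR dyads; 20 interviews in all; the number held after month 3 is given only as some.
- Assumption: some of 20 means at least 1 and at most 19.
- Share of the SR arm: 1/50 = 2% to 19/50 = 38%.
- Share of all dyads: 1/100 = 1% to 19/100 = 19%.
- Controls: 0.
- If all 20 were held early: 20/50 = 40% of the SR arm and 20/100 = 20% of all dyads.

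These are bounds, not estimates. The count is 0 if different people do the two tasks, and it falls if some of these dyads never reach a 6-month survey.

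**Step 5: how long the RA could know the arm** (taking 30.4 days per month)

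- Longest, with the interview just after an on-time 3-month survey: 6 − 3 = 3 months before the scheduled 6-month survey.
- To a disposition contact made 7 days ahead of that survey: 3 − 7/30.4 = 2.77 months.
- A shorter example, with the 3-month survey returned after 3 weeks of reminders (21/30.4 = 0.69 month) and the interview 1 month later: 6 − (3 + 0.69 + 1) = 1.31 months.

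The last figure is not a lower bound, because Section 5.2 allows surveys to be completed outside the planned window.

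**The case against.** The strongest reply is that little follows from the gap. Surveys are completed by participants online or by mail, participants know their arm, and no section has the RA rate a follow-up outcome. The remaining contacts leave limited discretion: reminders run on fixed weeks, and the disposition survey only establishes whether the person with memory concerns has moved or died. A participant could also reveal the arm in any telephone call, so reassigning interviews would not guarantee blinding. This stands, and it limits the weight of the point. It does not make the blinding statement true.

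A second reply is that the overlap may never occur. Two RAs were added, and Section 22.1 also names the coordinator, alongside the RA, for resending consent forms around the interview. The month-3 option was introduced because of funding and timeline limits, so some of these dyads may never reach a 6-month survey. All of this is possible, but the text that assigns the interviews still names the research assistant and divides nothing.

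A third reply concerns the capacity assessment (UBACC) at 6 months, for which Section 22.1 names no assessor. Its score is read against a fixed cutoff of 14.5 and decides between consent and assent, and Section 10.2.2 includes people with or without capacity. It is therefore a weak route for bias, and the finding does not depend on it.

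**Conclusion.** The concern holds as a defect in the written plan. RA blinding at the 6-month follow-up is asserted without exception, yet the role said to be blinded is assigned SR-only interviews that may come first.

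The documents do not show that unblinding happened. That would require the same person to do both tasks for a dyad that goes on to the 6-month survey. On that assumption, the affected dyads are bounded at 1 to 19 (or 20 if every interview were early), all in the SR arm. Control dyads, SR dyads interviewed only after their 6-month survey and dyads that never reach that survey are unaffected.

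The effect on outcomes is likely modest, and neither its size nor its direction can be estimated from the documents. Confidence is high about the textual gap, but that confidence does not extend to actual bias. The point should be corrected because the correction is cheap and the blinding claim may otherwise be reported wrongly.

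**What to change.** **Preferred.** In Section 5.2 (item 8 and both places in Phase II Data Collection that describe the interviews), state that any interview held before a dyad's 6-month survey is scheduled and conducted by existing staff with no 6-month follow-up contact with that dyad. Keep the interview list, recordings and notes from the follow-up RA until that dyad's 6-month data are in. Three staffing options are available, each with a cost:

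- A second RA adds no new role, but must stay off that dyad's 6-month contacts.
- A co-investigator already takes part in selecting SR dyads, but Section 20.1 gives the co-investigators oversight of data management and analysis.
- The coordinator already knows assignments, but would have to stay off that dyad's 3-week call. Some courtesy bias is possible, because the coordinator arranges the SR introduction.

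**Alternative.** Leave the staffing as it is and exclude dyads interviewed before their 6-month survey from the RA-blinding statement. This costs only wording and still works if such interviews have already taken place.

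**In either case.** Record and report how many dyads were interviewed after month 3 and by which role. Naming the role that does the 6-month UBACC and re-consent for these dyads would be a useful clarification, but is secondary.

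The total cost is a sentence or two in three places and, under the preferred option, reassignment of at most 19 interviews (20 if all were early). The documents do not give the staff time involved.

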6.0 Data Banking

6.1 Storage and Access: Any datasets generated and/or analyzed and published or placed in a data repository will be de-identified.

6.2 Data: See 6.1.

6.3 Release/Sharing: All information obtained from the participants will remain strictly confidential and will not be released except at the express written request of the study participant [unless permitted by law or regulatory oversight].

7.0 Sharing of Results with Participants

7.1 A report of the study findings will be provided to participants via an infographic. The report will only include aggregated findings and de-identified participant quotes (no other individual-level data).

8.0 Study Duration

SOCIAL PROTOCOL (HRP-580)

PROTOCOL TITLE: A Mobile Informatics Solution to Aid in Memory

VERSION DATE: 7/1/2022

8.1 Phase I: Each individual participant will take part in Phase I of the study one time for a dyadic interview. We anticipate taking 6 months to enroll all 20 participants. We expect all study procedures and data analysis to take 12 months total.

Phase II: Each participant will take part in the study for a total of about 6 months (data collection at enrollment, 3, and 6 months). We anticipate taking 12 months to enroll all 100 dyads. All study procedures and data analysis are anticipated to be completed within 24 months.

